[name] brings over 20 years' experience to the current study. She has the experience and skills to ensure timely completion of all the project milestones, organize communications among investigators, ensure regulatory and IRB compliance, overs study and effectively multi-task the various administrative duties associated with large complex studies. She also contributes to manuscripts for publication and data presentations at scientific meetings.

- **[name] RN (AMC Study Coordinator and Dialysis Center staff)**

[name] has over 16 years' experience in dialysis access and hemodialysis therapy. She is CITI certified and is highly skilled at recruiting, enrolling and retaining participant's in previous studies. She has demonstrated that she can efficiently and effectively coordinate the flow of participants during their study visits to the CRC, reinforce compliance with study interventions, collect and retain data in a well-organized manner, and maintain updated regulatory documentation and case report forms.

Recruitment Methods

Study staff will identify potential subjects from dialysis centers mentioned above. Subjects will be approached for a brief conversation to establish if there is interest in hearing about the study. If the patient is interested, the study coordinator will then present a detailed explanation of the study.

Subjects who meet all of the inclusion criteria ascertained at the screening visit will be enrolled in the study. In order to reach the goal of 450 subjects who complete the protocol, we will screen up to 900 subjects with CKD, allowing for a screening to enrollment ratio of 2:1. Once the target enrollment is complete we will discontinue screening irrespective of whether we have yet to reach 900 subjects.

Study team members who approach patients at centers will be very careful of explaining to potential subjects that research participation is completely voluntary and that their decision whether to participate or not, will have no impact in their medical care. Also, participants will receive a full explanation of the extent of their participation in the study prior to signing the informed consent form.

Hemodialysis Access Surveillance Evaluation (HASE) Study

Number of Subjects

450 Patients.

Confidentiality

Patients' identifying information will be stored in a password-protected, firewall enabled database, only available to approved study staff. The database will be kept for the duration of the study.

All subjects will be assigned a unique study number, and a Master Key spreadsheet linking the subject's name and medical record number to the study number will be kept by the principal investigator in a password-protected and firewall enabled file. Only personnel specifically involved in the conduct of the study, including the PI and research coordinators, will have access to the spreadsheet linking the unique study number to identifiable patient information. All data and questionnaires obtained from subjects will be labeled with their unique study numbers, and only study personnel will have access to the database than can link data with subject identifiable information. All hard copies of data such as questionnaires will include only the subject's unique study number to protect subject privacy and will be stored by the research coordinator in locked offices at the Dialysis Clinic Inc. located at [name] while the study is active. Only the research coordinator will have access to the records. The offices are monitored by security personnel and require electronic keys to be accessed. Once the study is completed all study documents will be archived by the PI at Albany Medical College.

Study personnel will receive training to secure understanding of the importance of protecting subject privacy and the appropriate handling of subject protected health information. At a minimum, this will include all mandatory training required by the Albany Medical College and the Subjects Human Research Office.

Provisions to Protect the Privacy Interests of Subjects

As was mentioned before, study team members who approach patients at centers will be very careful of explaining to potential subjects that research participation is completely voluntary and that their decision whether to participate or not, will have no impact in their medical care. Also, participants will receive a full explanation of the extent of their participation in the study prior to signing the informed consent form. They will be explained that if they want to stop participation at any time, they may do so without any consequences.

Patients will be given ample opportunity to voice any particular limitations or objections they have to participation previous to signing the informed consent form and their requests will be taken into consideration at the moment of decision to include them in the study.

Hemodialysis Access Surveillance Evaluation (HASE) Study

Consent Process

Written, informed consent to participate in the study will be obtained by a qualified, authorized member of the study team as determined by the IRB and the Principal Investigator; a process that will take place prior to carrying out any study procedures.

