Robbin et al 2006 (18)	126	
 • Duplex Scan (Ultrasound) 	AVG	AVG Survival	Not beneficial
Tessitore et al. 2004	79	
 • Access flow 	AVF	Thrombosis	Beneficial

Study Design

Randomized, Prospective Clinical Trial. Patients, PI, funder (Transonic) and statistician blinded (this will be implemented in Velos). Intervention and standard of care are different and cannot be blinded from attending nurses or clinic personnel. If a patient needs to switch schedules, they need to switch to shift that matches their protocol. Otherwise, they will need to switch protocols. No Transonic (funding) personnel will be involved in study design, protocol, analysis, or publication.

Randomization:

Patient is consented, baseline assessment taken, and evaluated for inclusion before randomization (baseline data will be included in analysis to determine representativeness of study patients to clinic patients). Randomization will occur after enrollment period ends.

The intervention and control protocols are significantly different that individual patients in the same dialysis session would be able to identify which arm they are in. Therefore, blocks of patients will be randomized according to dialysis schedule within each clinic.

Hemodialysis Access Surveillance Evaluation (HASE) Study

Because the staffing is similar across shifts, we will do block randomization where all patients in a shift are assigned to the same protocol at each clinic site. For each clinic, the blocks will be given a number based on chronological order (Monday 1st shift = 1, Monday 2nd shift = 2 +, Monday 3rd shift = 3, Tuesday 1st shift = 4, Tuesday 2nd shift = 5, Tuesday 3rd shift = 6). For each clinic site, a coin will be flipped in front of two witnesses: heads = first group treatment; tails = first group control. Then a die will be rolled. The number that is rolled will the first group assigned (based on coin toss). The remaining groups will be allocated in sequence. For instance, if the coin lands on heads and the die lands on 3, Monday 3rd shift is intervention, Tuesday 1st shift is control, Tuesday 2nd shift is intervention, Tuesday 3rd shift if control, Monday 1st shift is intervention and Monday 2nd shift is control. If a patient has to switch dialysis schedules, care must be taken to place them in the same arm.

Inclusion and Exclusion Criteria

Inclusion criteria:

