Chronic hemodialysis patients undergoing dialysis therapy via an upper extremity arteriovenous access (arteriovenous fistula or an arteriovenous graft) will be enrolled to have monthly surveillance flow measurement using Transonic system or physical examination of the arteriovenous access by qualified person at least once a month for a period of 2 years.

Exclusion criteria:

- Patients requiring surgical intervention on the arteriovenous access.
- History of access thrombosis (one or more access thrombosis of the current AV access).
- Patients with signs of access infection.
- Patients with a malignancy.
- Patients with life expectancy of less than six months.
- Unable to understand the study.
- Unable to sign the consent form.
- Patients with psychiatric disorder.
- Age less than 18 or greater than 80 years.
- Adults unable to consent
- Individuals who are not yet adults (infants, children, teenagers)
- Pregnant women
- Prisoners

Procedures Involved

Chronic hemodialysis patients receiving treatment with an upper extremity arteriovenous access will be enrolled in this 2 year study. End of study starts as last patient from 450 completes follow-up. Patients would be randomly assigned into surveillance or the control group. Randomization will take a cluster pattern per shift. (shift randomization).

Hemodialysis Access Surveillance Evaluation (HASE) Study

Surveillance group

- a. Surveillance group would receive monthly blood flow surveillance by ultrasound dilution technique (using the Transonic system) plus standard care (see below). Patients would be referred for an intervention based on the current KDOQI recommendations i.e. access flow of less than 600 ml/minute for arteriovenous grafts and less than 500 ml/minute for patients with arteriovenous fistulas or if the access flow is 1000 ml/minute that has decreased by more than 25% over 4 months (1). In addition to the detection of access dysfunction, the time interval between the detection of access dysfunction by the Transonic system and the intervention will also be recorded.

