H_{0-1} : Patients screened monthly with UDT and followed up with proactive intervention (if clinically indicated) will not have a time to thrombosis that is different than patients receiving physical examination and reactive intervention (if clinically indicated)

H_{0-2} : Patients screened monthly with UDT and followed up with proactive intervention (if clinically indicated) will not have a number of angioplasty procedures that is different than patients receiving physical examination and reactive intervention (if clinically indicated)

H_{0-3} : Patients screened monthly with UDT and followed up with proactive intervention (if clinically indicated) will not have a number of thrombectomy procedures that is different than patients receiving physical examination and reactive intervention (if clinically indicated)

H_{0-4} : Patients screened monthly with UDT and followed up with proactive intervention (if clinically indicated) will not have a rate of tunneled dialysis catheter (TDC) that is different than patients receiving physical examination and reactive intervention (if clinically indicated)

H_{0-5} : Patients screened monthly with UDT and followed up with proactive intervention (if clinically indicated) will not have a rate of non-tunneled dialysis catheter (non-TDC) that is different than patients receiving physical examination and reactive intervention (if clinically indicated)

Sample Size:

$\alpha = 0.05$, $\beta = 0.80$, 2-sided (testing benefit and harm)

Main predictor: Treatment or control; Main outcome: Thrombosis or no—two-sided therefore chi-square for proportions of dichotomous variables was used for sample size calculations.

Treatment versus control estimates of thrombosis (based on Tessitore 2004; Scaffaro 2009, Moist 2003, Robbin 2006, Sands 1999, Ram 2003, Tessitore 2008): 34% in control; 24% in treatment (effect size 30%); 342 per group; loss to f/u (move, transplant, different clinic) 5% = $1/(1-.5)=1.05=359$ (low estimate); loss to mortality 10% a year = 1.11 2x (per [name]) = 443

Variables to be collected at baseline:

age, sex, race (white, black, Asian/Pacific Islander, American Indian/Alaskan Native), ethnicity (Hispanic or not), insurance type (private, Medicaid, Medicare,

Hemodialysis Access Surveillance Evaluation (HASE) Study

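### The goal of 450 completers is in effect an enrolment figure: on the plan's own attrition rates about 346 patients would complete 24 months

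*Combined protocol and SAP*

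**What the plan says.** Four parts of the protocol bear on this point.

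- **Recruitment Methods** sets the target in terms of completers: "In order to reach the goal of 450 subjects who complete the protocol, we will screen up to 900 subjects with CKD". It continues, "allowing for a screening to enrollment ratio of 2:1". The next sentence ends screening once target enrolment has been reached, even if fewer than 900 have been screened.
- **Number of Subjects** gives 450 patients, without saying whether these are enrolled or completing.
- **Procedures Involved** describes a 2-year study.
- **Data Management, Sample Size** starts from "34% in control; 24% in treatment (effect size 30%); 342 per group". It then inflates for 5% loss to follow-up (moves, transplants, change of clinic) and for "loss to mortality 10% a year", applied twice, and arrives at 443.

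**The concern.** Recruitment Methods uses 450 for two different quantities. By its own ratio and screening limit it is the number enrolled; by its wording it is the number who finish. The two coincide only if nobody dies or leaves in 2 years, and the Sample Size section assumes that patients will do both. I found no provision in the available text for replacing patients who leave.

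At stake is what a reader takes the trial's size to be. Someone relying on Recruitment Methods would expect 450 patients with full follow-up, about 30% more than the plan's own rates support (450/346 = 1.30). The ambiguity also hides how far the recruitment figure lies from the per-group numbers in the Sample Size section.

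**Working it through.** **Inputs.** From Sample Size: 34% v 24%, two-sided alpha 0.05, power 0.80 (printed as beta), 342 per group, 5% loss applied once, 10% mortality a year applied for two years. From Recruitment Methods: 450, 900 and 2:1. From Procedures Involved: 2 years.

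**1. The plan's own figures.** The section says that "chi-square for proportions of dichotomous variables was used for sample size calculations". The two-proportion formula with pooled variance under the null, p̄ = 0.29, gives

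n = [1.96 × √(2 × 0.29 × 0.71) + 0.8416 × √(0.34 × 0.66 + 0.24 × 0.76)]² / 0.10² = 322.04, which rounds up to 323.

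With the continuity correction,

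n′ = (322.04/4) × [1 + √(1 + 4/(322.04 × 0.10))]² = 341.7, which rounds up to 342, as stated.

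Inflation: 342 × 1.05 = 359, and 359/0.90² = 443.2, matching the stated 443 (359 × 1.11² = 442.3). The printed divisor for the 5% loss, (1 − .5), is a slip for (1 − .05); the factor of 1.05 shows what was meant. The attrition rates are therefore read as the plan used them, and 443 is a number to enrol.

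**2. Enrolment implied by Recruitment Methods.** 900/2 = 450.

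**3. Completers from 450 enrolled.**

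- 450 × 0.95 × 0.90 × 0.90 = 346.3. The shortfall is 450 − 346 = 104, and 104/450 = 23%.
- With the plan's rounded factors: 450/(1.05 × 1.11 × 1.11) = 450/1.294 = 348.
- If losses are added instead of multiplied: 450 × (1 − 0.05 − 0.19) = 342, or 450 × (1 − 0.05 − 0.20) = 337.5.
- If the 5% loss is taken as yearly: 450 × 0.95² × 0.81 = 329.

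Every reading falls between 329 and 348. None approaches 450.

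**4. What 450 completers would need.** 450/(0.95 × 0.81) = 584.8, so about 585 enrolled. At 2:1 that is about 1,170 screened, above the limit of 900.

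**5. Against the Sample Size section**, assuming two equal arms:

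- Completers: 346/2 = 173 per arm, against 342 evaluable per group.
- Enrolled: 450/2 = 225 per arm, against 443 per group.

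**The case against.** The strongest reply is that this is one loose word. The division of 900 by 2 is correct, and the stop rule and Number of Subjects read most naturally as enrolment. Since 443 lies close to 450, the authors may have taken 450 as a figure already inflated for attrition, so that the word for completing is a drafting slip. That may well be so, but it is inference. It supports the correction, because 450 should then be labelled as enrolled. It also exposes the larger difficulty that 443 was derived from 342 per group, while 450 is a total.

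A second reply is that completing the protocol is never defined, and that patients who clot early, die or transfer still contribute to the Kaplan-Meier and Cox analyses. This stands in part. The 23% is a shortfall against a stated number of completers; it is not shown to be an equal loss of information. But the Sample Size section treats deaths and departures as losses to be made good, so counting them as completions would contradict it.

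A third is that no single sentence closes enrolment at 450. That is true. The screening limit, the ratio and Number of Subjects together imply it, and the stop rule fits.

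Three stronger readings are tempting and are not supported:

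- **Sites would add patients after allocation to reach 450 completers, opening selection bias.** The Randomization section says "Randomization will occur after enrollment period ends", Recruitment Methods stops screening at target enrolment, and nothing I found allows later additions.
- **The trial cannot end until 450 patients complete.** Procedures Involved says "End of study starts as last patient from 450 completes follow-up". This reads naturally as the last patient of the enrolled cohort to finish follow-up; it does not require 450 completions.
- **Deaths during a 3 to 6 month wait for randomisation cut the figure to 329–337.** That makes every patient wait the whole enrolment period. With even accrual the mean wait is 1.5 to 3 months. Mortality is then 1 − 0.9^0.125 = 1.3% to 1 − 0.9^0.25 = 2.6%, which leaves about 337 to 342. Even this assumes that the 24 months start at randomisation, which the text does not clearly say.

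**Conclusion.** The contradiction holds. Recruitment Methods promises 450 completers from recruitment figures that yield about 450 enrolled. On the plan's own rates about 346 would complete 24 months (348 with its rounded factors), roughly 104 or 23% fewer than stated.

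This rests on three assumptions: completing the protocol means 24 months of follow-up, the 5% loss applies once over the study, and mortality is 10% in each of two years. Other readings of the losses move the result only within 329 to 348.

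The point concerns how the trial's size is stated. It does not show a recruitment bias, an unreachable end of study, or a 23% loss of information on the primary outcome. The corrected figure cannot be left on its own, because about 173 completers per arm (equal arms assumed) does not meet the 342 evaluable per group that the Sample Size section requires.

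**What to change.** 1. In Recruitment Methods, describe 450 as the number enrolled and add that, at 5% loss to follow-up and 10% mortality a year, about 346 are expected to complete 24 months. Label the 450 under Number of Subjects as enrolled.
2. Reconcile both figures with the Sample Size section: say whether 342 and 443 are per group, and explain how a total of 450 enrolled relates to them. If the total changes, recompute the expected completers with the same factors.

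Raising enrolment to about 585 so that 450 complete would not settle the second item. It gives 225 completers per arm, and power for 34% v 24% of about 65% (normal approximation, equal arms, no continuity correction, no allowance for randomising by shift).

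The restatement costs wording only and requires no extra patients; its downside is that a stated figure becomes less favourable. Whether the total itself should change is a separate decision that the reconciliation will bring into view.
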